## 4. STUDY SCHEMATIC AND SCHEDULE OF ACTIVITIES

### 4.1. Study Schematic

Figure 1: 997HA402 Study Design

Abbreviations: ITI=immune tolerance induction; Max=maximum.

Only subjects who achieve ITI success within the 48-week (12-month) ITI Period will continue into the Tapering and Follow-Up Periods. During the Tapering and Follow-Up Periods, the subject's dose will be adjusted to achieve the prophylactic dose. However, if FVIII peak activity levels rise above 200 IU/dL after the inhibitors are negative but before all the ITI success criteria are met, the dose may be adjusted according to Investigator judgment to maintain the FVIII peak activity levels between 100 and 200 IU/dL. This dose reduction will not be considered part of the Tapering Period, and the subject will maintain the schedule of assessments per the ITI Period. See Section 11.1 for dosing details.

CONFIDENTIAL

The information contained herein may not be used, disclosed, or published without the written consent of Bioverativ Therapeutics Inc.

Page 19

## 4.2. Schedules of Activities

**Table 1: Schedule of Activities for Screening Visit and ITI Period**

Activities	Screening Visit	ITI Period				EOT for Partial Success or Failure 	
		Baseline Visit (within 4 weeks of Screening)	Week 2 Visit	Interim ITI Visits	ITI Outcome Assessment Visit	EOT Visit	Final Safety Follow-Up
		Start of ITI treatment	2 weeks ( $\pm 3$ days) from start of ITI treatment	Every 4 th week ( $\pm 1$ week) Starting at ITI Week 4 until first negative titer (<0.6 BU/mL) is achieved OR 48 weeks of ITI treatment 	Every 2 nd week ( $\pm 3$ days) Starting at time of first negative inhibitor titer until ITI success OR 48 weeks of ITI treatment		7 to 14 days after EOT Visit
Informed Consent or Assent Form	X						
Assessment of Subject Eligibility	X						
Demographics	X						
Medical, Surgical, Hemophilia, Inhibitor, Bleeding Episodes, and ITI History	X						
Physical Examination	X	X	X	X	X	X	
Height (cm)	X					X	
Weight (kg)	X	X	X	X	X	X	
Vital Signs 	X	X	X	X	X	X	

CONFIDENTIAL

The information contained herein may not be used, disclosed, or published without the written consent of Bioverativ Therapeutics Inc.

Activities	Screening Visit	ITI Period				EOT for Partial Success or Failure 	
		Baseline Visit (within 4 weeks of Screening)	Week 2 Visit	Interim ITI Visits	ITI Outcome Assessment Visit	EOT Visit	Final Safety Follow-Up
		Start of ITI treatment	2 weeks ( $\pm 3$ days) from start of ITI treatment	Every 4 th week ( $\pm 1$ week) Starting at ITI Week 4 until first negative titer (<0.6 BU/mL) is achieved OR 48 weeks of ITI treatment 	Every 2 nd week ( $\pm 3$ days) Starting at time of first negative inhibitor titer until ITI success OR 48 weeks of ITI treatment		7 to 14 days after EOT Visit
Hematology (Local Laboratory) 	X	X		X	X	X	
Blood Chemistry (Local Laboratory) 	X	X		X	X	X	
Urinalysis (Local Laboratory) 	X	X		X	X	X	
Viral Analysis (HIV, HCV, and HBV) (Central Laboratory) 	X						
Blood Sample for Analysis of FVIII Mutation and HLA Allotyping (Central Laboratory) (Optional) 		X					
rFVIIIFc Dosing 		X	X	X	X	X	

CONFIDENTIAL

The information contained herein may not be used, disclosed, or published without the written consent of Bioverativ Therapeutics Inc.

Activities	Screening Visit	ITI Period				EOT for Partial Success or Failure 	
		Baseline Visit (within 4 weeks of Screening)	Week 2 Visit	Interim ITI Visits	ITI Outcome Assessment Visit	EOT Visit	Final Safety Follow-Up
		Start of ITI treatment	2 weeks ( $\pm 3$ days) from start of ITI treatment	Every 4 th week ( $\pm 1$ week) Starting at ITI Week 4 until first negative titer (<0.6 BU/mL) is achieved OR 48 weeks of ITI treatment 	Every 2 nd week ( $\pm 3$ days) Starting at time of first negative inhibitor titer until ITI success OR 48 weeks of ITI treatment		7 to 14 days after EOT Visit
Nijmegen-Modified Bethesda Inhibitor Assay (Both Local and Central Laboratories) 	X	X	X		X	X	
Anti-rFVIIIFc Antibody (ADA) (Central Laboratories) 	X	X		X	X	X	
Blood Sample for Immune Cell Characterization (Central Laboratory) 		X		X		X	
FVIII Activity Level (Both Local and Central Laboratories) 			X	X	X	X	
FVIII Activity for IR (Both Local and Central Laboratories) 					X		

CONFIDENTIAL

The information contained herein may not be used, disclosed, or published without the written consent of Bioverativ Therapeutics Inc.

Page 22

Activities	Screening Visit	ITI Period				EOT for Partial Success or Failure 	
		Baseline Visit (within 4 weeks of Screening)	Week 2 Visit	Interim ITI Visits	ITI Outcome Assessment Visit	EOT Visit	Final Safety Follow-Up
		Start of ITI treatment	2 weeks ( $\pm 3$ days) from start of ITI treatment	Every 4 th week ( $\pm 1$ week) Starting at ITI Week 4 until first negative titer (<0.6 BU/mL) is achieved OR 48 weeks of ITI treatment 	Every 2 nd week ( $\pm 3$ days) Starting at time of first negative inhibitor titer until ITI success OR 48 weeks of ITI treatment		7 to 14 days after EOT Visit
FVIII Activity for $t_{1/2}$ Evaluation (Both Local and Central Laboratory) 					X	X	
EPD Review, Including Review of Bleeding Episodes and rFVIIIFc Dosing Accountability 		X	X	X	X	X	
Nonserious Adverse Events		X	X	X	X	X	X
Serious Adverse Events 	X	X	X	X	X	X	X
Concomitant Therapy/Procedures Recording	X	X	X	X	X	X	X

Abbreviations: ADA=anti-drug antibody; BU=Bethesda Unit; EOT=end of treatment; EPD=electronic patient diary; FVIII=coagulation factor VIII; HBV=hepatitis B virus; HCV=hepatitis C virus; HIV=human immunodeficiency virus; HLA=human leukocyte antigen; ICF=informed consent form; IR=incremental recovery; ITI=immune tolerance induction; rFVIIIFc=recombinant coagulation factor VIII Fc fusion protein;  $t_{1/2}$ =half-life.

NOTE: inhibitor titer, FVIII activity level,  $t_{1/2}$ , and IR are all assessed at the local laboratory, with confirmation by the central laboratory. The Investigators will use local laboratory results for decision-making purposes. Hematology, blood chemistry, and urinalysis are assessed only at the local laboratory.

CONFIDENTIAL

The information contained herein may not be used, disclosed, or published without the written consent of Bioverativ Therapeutics Inc.

-  Subject will be allowed to get the confirmatory test, even if it is after the 48-week (12-month) period, as long as the first test occurred during the 48-week (12-month) period. If the second test confirms the results of the first test (<0.6 BU/mL), the date of ITI outcome will be the date of the first value, which occurred during the 48-week (12-month) period. Fluctuations in inhibitor levels is common and variability in inhibitor titer is expected. Subjects will be treated on a case-by-case basis.
-  If, after the initial 3 months (12 weeks), there is no downward trend (at least 20% in the inhibitor titer) over a 6-month (24-week) period that is assessed at the Week 36 interim ITI Visit, the subject will be considered a treatment failure and must complete the EOT Visit as soon as possible. The second (confirmatory) inhibitor test will occur 2 weeks after the first negative inhibitor test.
-  Vital signs include blood pressure, pulse rate, respiratory rate, and body temperature. In the event of in-clinic rFVIIIFc injections, assessments will be taken prior to and 20 ( $\pm$ 5) minutes after the end of the rFVIIIFc injection (if dosing occurs at the visit).
-  Blood samples for determination of hematology and blood chemistry variables and urine dipstick will be collected at Screening Visit, Baseline Visit (before the first study treatment administration), and then every 12 weeks (3 months) from the start of the ITI Period through the time of ITI complete success. If the subject completes the ITI Period in a duration shorter than 12 weeks (3 months), these assessments must be completed at the end of the ITI Period.
-  Dipstick urinalysis, including a protein reading; if the protein reading is positive ( $\geq$ 1+), a full laboratory urinalysis will be required.
-  Sample will be collected and tested if there are no HIV testing results available in the medical history 26 weeks (6.5 months) prior to Screening. HCV and HBV will only be tested at Screening if there is any indication in the medical record that the subject has prior exposure to plasma-derived coagulation factors. For subjects without prior exposure, the sample will be collected and stored at the central laboratory. If the subject is diagnosed with HBV or HCV during the study, this sample will be analyzed by the central laboratory to determine seropositivity at Screening.
-  This assessment is optional, and requires a separate ICF. For subjects whose FVIII mutation and human leukocyte antigen (HLA) allotype is not documented in medical records, samples for analysis of FVIII mutation and HLA allotyping will be collected at the Baseline Visit or at any subsequent visit if blood volume is limited at the Baseline Visit for analysis at the central laboratory.

For Canada specific requirements: see Appendix B.

-  Clinic dosing is applicable only if warranted.
-  Subjects will be advised to delay administration of their daily dose of rFVIIIFc until after the sample for inhibitor testing is taken. For sites that have not yet adopted the Nijmegen-Modified Bethesda Assay, use of the Bethesda Assay is acceptable.
-  A whole blood sample will be collected at Baseline OR Screening, every fourth week during interim ITI Visits, during assessment of ITI outcome visits, and at EOT. A sample for Anti-rFVIIIFc Antibody (ADA) should be collected at Baseline or Screening, and each consecutive visit, except the Week 2 and Safety Follow-Up Visits when allowed by the total volume of plasma that can be collected in one day.
-  A whole blood sample will be collected at ITI Day 1 (Baseline Visit, predose) and at Week 8 (Month 2), as allowable based on subject weight and institutional practice regarding blood draw restrictions for pediatric subjects.
-  A sample for FVIII activity will be collected at visits where samples for IR or  $t\frac{1}{2}$  assessments are not collected.
-  IR assessment will only be performed after a negative inhibitor has been confirmed at 2 consecutive visits. The sample for IR is drawn at the visit for the confirmatory negative inhibitor titer. However, the interpretation of the IR result will be performed after the negative inhibitor titer is confirmed. The predose sample for IR calculations is to be taken when the subject is in a nonbleeding state and after at least a 24-hour washout. See [Table 3](#) for details. Subjects will be advised to delay administration of their daily dose of rFVIIIFc until after the sample for IR testing is taken
-  Subjects will be advised to delay administration of their daily dose of rFVIIIFc until after the sample for  $t\frac{1}{2}$  is taken. Half-life determination will only be performed after IR  $\geq$ 1.32 IU/dL per IU/kg has been confirmed at 2 consecutive visits or as part of the EOT Visit.  $t\frac{1}{2}$  determinations are to be performed

CONFIDENTIAL

The information contained herein may not be used, disclosed, or published without the written consent of  
Bioverativ Therapeutics Inc.

Page 24

when the subject is in a nonbleeding state and after at least a 24-hour washout.  $t_{1/2}$  determination at EOT Visit does not need to be performed if the full 4-sample  $t_{1/2}$  assessment was performed within 2 weeks prior to the EOT Visit or if the Investigator determines the subject is an ITI Treatment Failure.

 It is recommended that subjects/caregivers enter dosing information immediately after an injection or within a maximum of 7 days.

 Serious adverse events are to be monitored and recorded from the time of signing of the ICF.

CONFIDENTIAL

The information contained herein may not be used, disclosed, or published without the written consent of  
Bioverativ Therapeutics Inc.

Page 25

VV-CLIN-0542000 3.0

**Table 2: Schedule of Activities for the Tapering and Follow-Up Periods After Successful Tolerization**

Activities	Tapering Period 	Follow-Up Period 	EOT 	
	Tapering Initiation Visit/Telephone Call,  Week 2, 4, 8, 12, and 16 Visits	Week 28 and 40 Visits 	EOT Visit	Final Safety Follow-Up
	Starting at ITI success and continuing for a minimum of 16 weeks with visits after 2 weeks ( $\pm 3$ days), 4 weeks ( $\pm 1$ week), and then every 4 th week ( $\pm 1$ week)	Week 28 and 40 visits ( $\pm 2$ weeks)  following ITI success	Week 48 visit ( $\pm 2$ weeks) following ITI success OR upon relapse	7 to 14 days after EOT Visit
Physical Examination	X	X	X	
Height (cm)			X	
Weight (kg)	X	X	X	
Vital Signs 	X	X	X	
Hematology (Local Laboratory) 	X		X	
Blood Chemistry (Local Laboratory) 	X		X	
Urinalysis (Local Laboratory) 	X		X	
Nijmegen-Modified Bethesda Inhibitor Assay (Both Local and Central Laboratories) 	X	X	X	
Anti-rFVIIIFc Antibody (ADA) (Central Laboratory)	X	X	X	

CONFIDENTIAL

The information contained herein may not be used, disclosed, or published without the written consent of Bioverativ Therapeutics Inc.

Activities	Tapering Period 	Follow-Up Period 	EOT 	
	Tapering Initiation Visit/Telephone Call,  Week 2, 4, 8, 12, and 16 Visits	Week 28 and 40 Visits 	EOT Visit	Final Safety Follow-Up
	Starting at ITI success and continuing for a minimum of 16 weeks with visits after 2 weeks ( $\pm 3$ days), 4 weeks ( $\pm 1$ week), and then every 4 th week ( $\pm 1$ week)	Week 28 and 40 visits ( $\pm 2$ weeks)  following ITI success	Week 48 visit ( $\pm 2$ weeks) following ITI success OR upon relapse	7 to 14 days after EOT Visit
Blood Sample for Immune Cell Characterization (Required) (Central Laboratory) 	X		X	
rFVIIIFc Dosing 	X	X	X	
FVIII Activity for IR (Both Local and Central Laboratories) 	X	X		
FVIII Activity for $t_{1/2}$ Evaluation (Both Local and Central Laboratories) 			X	
FVIII Activity Level (Both Local and Central Laboratories) 		X	X	
EPD Review, Including Review of Bleeding Episodes and rFVIIIFc Dosing Accountability 	X	X	X	
Nonserious Adverse Events	X	X	X	X
Serious Adverse Events	X	X	X	X

CONFIDENTIAL

The information contained herein may not be used, disclosed, or published without the written consent of Bioverativ Therapeutics Inc.

Page 27

Activities	Tapering Period 	Follow-Up Period 	EOT 	
	Tapering Initiation Visit/Telephone Call,  Week 2, 4, 8, 12, and 16 Visits	Week 28 and 40 Visits 	EOT Visit	Final Safety Follow-Up
	Starting at ITI success and continuing for a minimum of 16 weeks with visits after 2 weeks ( $\pm 3$ days), 4 weeks ( $\pm 1$ week), and then every 4 th week ( $\pm 1$ week)	Week 28 and 40 visits ( $\pm 2$ weeks)  following ITI success	Week 48 visit ( $\pm 2$ weeks) following ITI success OR upon relapse	7 to 14 days after EOT Visit
Concomitant Therapy/ Procedures Recording	X	X	X	X

Abbreviations: EOT=End of Treatment; EPD=electronic patient diary; ET=early termination; FVIII=coagulation factor VIII; IR=incremental recovery; ITI=immune tolerance induction; PK=pharmacokinetic; rFVIIIFc=recombinant coagulation factor VIII Fc fusion protein;  $t_{1/2}$ =half-life.

NOTE: inhibitor titer, FVIII activity level,  $t_{1/2}$ , and IR are all assessed at the local laboratory, with confirmation by the central laboratory. The Investigators will use local laboratory results for decision-making purposes.

Hematology, blood chemistry, and urinalysis are assessed only at the local laboratory.

- 1 During the Tapering and Follow-Up Periods, the subject's dose will be adjusted to achieve each subject's prophylactic dose as determined by the Investigator. Minimum Tapering Period is 16 weeks (4 months). Subjects who relapse during the Tapering Period (i.e., who have confirmation of inhibitor development AND who have confirmed decrease of IR, with or without clinical signs or symptoms) will proceed immediately to the EOT Visit. Subjects will be closely monitored during the Tapering Period for potential relapse.  
For Canada specific requirements: see Appendix B.
- 2 Timing of the EOT Visit will vary for subjects, as described in Section 7.2.6.
- 3 Once  $t_{1/2}$  has been determined to be  $\geq 7$  hours, the Investigator may elect to have a Tapering Initiation Visit and/or a Tapering Initiation Telephone Call. If the subject has already begun downtitration from the 200 IU/kg/day ITI dose prior to ITI success, the subject will return for the next scheduled visit (the Tapering Initiation Visit) 2 weeks from the visit at which  $t_{1/2}$  was determined to be  $\geq 7$  hours. If the subject has not already downtitrated when  $t_{1/2}$  is determined to be  $\geq 7$  hours, the Investigator can make a telephone call to instruct the subject to begin downtitrating immediately (Tapering Initiation Telephone Call) Subject's subsequent visit, which will occur 2 weeks from the visit at which  $t_{1/2}$  was determined to be  $\geq 7$  hours, will be the Tapering Initiation Visit (see Section 7.2.3).
- 4 Subjects who do not achieve ITI success within 48 weeks (12 months) will proceed to the ET/EOT Visit. Subjects who develop inhibitors during the Tapering or the Follow-Up Period (i.e., who relapse) will proceed immediately to the ET/EOT Visit.
- 5 Vital signs include blood pressure, pulse rate, respiratory rate, and body temperature. Postdose assessments following in-clinic injections will be taken prior to and 20 ( $\pm 5$ ) minutes after the end of the rFVIIIFc injection (if dosing occurs at the visit).
- 6 Hematology, blood chemistry, and urine dipstick are to be collected every 12 weeks (3 months) during the Tapering Period. These assessments will also be collected at the EOT Visit.
- 7 Dipstick urinalysis, including a protein reading; if the protein reading is positive ( $\geq 1+$ ), a full laboratory urinalysis will be required.

CONFIDENTIAL

The information contained herein may not be used, disclosed, or published without the written consent of  
Bioverativ Therapeutics Inc.

- 8 Subjects will be advised to delay administration of their daily dose of rFVIIIFc until after the sample for inhibitor testing is taken. An unscheduled visit may be required to repeat inhibitor testing under this protocol to obtain a sample to confirm a positive inhibitor test result.
- 9 If ITI success is declared, a sample will be collected at the first visit in the Tapering Period. If partial success or failure is declared, a sample will be collected at the EOT Visit. The samples will be collected as allowable based on subject weight and institutional practice regarding blood draw restrictions for pediatric subjects.
- 10 Takes place at each visit in which IR or  $t_{1/2}$  is being assessed.
- 11 Subjects will be advised to delay administration of the remainder of their daily dose of rFVIIIFc until after the sample for IR is taken. Blood samples will be collected for analysis of rFVIIIFc activity for assessment of IR starting at the visit for confirmed negative titers and at all consecutive visits, except for those visits where samples for rFVIIIFc  $t_{1/2}$  determination are drawn, as IR will be determined from the same samples. Blood samples will be taken at predose (within 30 minutes prior to the start of injection) and postdose ( $30 \pm 5$  minutes after the start of injection). If any assessments indicate the possibility of relapse at any time during the Tapering or Follow-Up Period, the test must be repeated at the following visit to confirm relapse (i.e., IR <66%).
- 12 Subjects will be advised to delay administration of the remainder of their daily dose of rFVIIIFc until after the final post-dose sample for  $t_{1/2}$  is taken (i.e., up to 48 hours post dose). PK assessments for  $t_{1/2}$  determination are to be performed when the subject is in a nonbleeding state and after at least a 24-hour washout (see [Table 3](#)).
- 13 A sample for FVIII activity can be collected as needed per Investigator discretion. FVIII activity levels can be derived from IR samples; therefore, a separate blood draw for FVIII activity assessment is not required.
- 14 It is recommended that subjects/caregivers enter dosing information immediately after an injection or within a maximum of 7 days.

CONFIDENTIAL

The information contained herein may not be used, disclosed, or published without the written consent of  
Bioverativ Therapeutics Inc.

Page 29

VV-CLIN-0542000 3.0

Details on sampling for rFVIIIFc are described in Section 13.1.3 and **Table 3**.

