### 6.2. Secondary Objectives and Endpoints

The secondary objectives are as follows:

- To describe the outcome of ITI treatment
- To describe the relapse rate over the 48-week (12-month) period following successful ITI performed with rFVIIIFc
- To describe the intercurrent bleeding during the ITI Period and during the 48-week (12-month) period after successful ITI performed with rFVIIIFc
- To describe the safety and tolerability of rFVIIIFc when used for ITI
- To evaluate the impact of ITI treatment with rFVIIIFc on health economics and adherence

The secondary endpoints are as follows:

- ITI success
  - Confirmed negative titers consisting of 2 consecutive negative inhibitor assessments within 2 weeks ( $\pm 3$  days) based on local laboratory results  $<0.6$  BU/mL by the Nijmegen-modified Bethesda assay; determination of negative titer based on the Bethesda assay is acceptable at sites that have not yet adopted the Nijmegen-modified Bethesda assay
  - IR  $\geq 1.32$  IU/dL per IU/kg in 2 consecutive assessments representing  $\geq 66\%$  of the expected IR 2 IU/dL per IU/kg ([SmPC](#); [USPI](#))
  - $t_{1/2} \geq 7$  hours
- Occurrence of relapse (defined as confirmed positive inhibitor titer  $\geq 0.6$  BU/mL), abnormal recovery after tolerance is achieved, and  $t_{1/2} < 7$  hours) during the Tapering or Follow-Up Periods
- Number of bleeding episodes during the ITI Period and during the 48-week (12-month) period after successful ITI performed with rFVIIIFc
- Adverse events (AEs) and serious adverse events (SAEs)

[figure not shown]
CONFIDENTIAL

The information contained herein may not be used, disclosed, or published without the written consent of  
Bioverativ Therapeutics Inc.

Page 36

- Number of days away from work or school
- Number of hospitalization days
- Adherence (defined as percentage of administered doses versus planned doses)
- Consumption of rFVIIIFc (measured in total rFVIIIFc use)

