### Relapse

If a subject experiences bleeding episodes that cannot be controlled with the use of rFVIIIFc, further investigation for relapse may be warranted.

Relapse is defined as the occurrence of the following (with or without clinical signs or symptoms) after complete ITI success, based on the International ITI criteria ([Hay & DiMichele, 2012](#)):

- A positive inhibitor ( $\geq 0.6$  BU/mL using the Nijmegen assay) on 2 consecutive assessments performed within 2 to 4 weeks; determination of positive titer based on the Bethesda assay is acceptable at sites that have not yet adopted the Nijmegen-modified Bethesda assay.

AND

- An IR  $<1.32$  IU/dL per IU/kg (representing  $<66\%$  of the expected IR) on 2 consecutive assessments performed within 2 to 4 weeks.

If any assessments indicate the possibility of relapse at any time during the Tapering or Follow-Up Period, the tests must be repeated at the following visit to confirm relapse. A subject with confirmed relapse (i.e., confirmation of both of the above criteria in 2 consecutive assessments) must complete the EOT Visit. At EOT,  $t_{1/2}$  will be assessed and recorded.

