### **7.2.5. Follow-Up**

After completion of the Tapering Period, subjects will enter the Follow-Up Period, during which subjects will be treated prophylactically with the rFVIIIFc dose and interval prescribed by the Investigator, according to the label and clinical response of the subject, for 32 weeks (8 months). To avoid bleeding episodes and a relapse of the inhibitors, FVIII activity levels should be kept  $\geq 1$  IU/dL.

If the subject experiences a bleeding episode during the Follow-Up Period, the treatment of the bleed will be left to the discretion of the Investigator. Treatment with bypassing agents may be considered if bleeding is unresponsive to treatment with rFVIIIFc. Subjects with bleeding episodes during the Follow-Up Period will be tested for recurrence of inhibitors (see Section [7.2.2.1](#)).

During the Follow-Up Period, the subject will visit the clinic every 12 weeks (3 months) and undergo procedures and assessments as per the schedule of activities (see [Table 2](#)). At each visit, samples for inhibitor titer and IR assessments will be drawn to monitor for relapse. A subject with confirmed relapse criteria will complete the EOT Visit as soon as possible.

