Subjects must not be currently bleeding and are required to have at least a 24-hour washout prior to the rFVIIIFc  $t_{1/2}$  predose sample collection. A dose of 50 IU/kg of rFVIIIFc for assessments will be delivered via a slow push IV injection over several minutes, at a rate of administration determined by the subject's comfort level. Volume and units of factor infused must be calculated and recorded using the actual potency as described in the DHA included in the Study Reference Manual. Subjects will not have any additional doses of rFVIIIFc during the PK Sampling Period. If emergency dosing is required during the  $t_{1/2}$  Sampling Period, inform the Sponsor and the  $t_{1/2}$  assessment will be rescheduled.

Once the final sample for  $t_{1/2}$  has been collected, the subjects can be given their daily ITI dose.

Subjects have fulfilled the third and last criterion for ITI success after a FVIII activity  $t_{1/2} \geq 7$  hours has been determined by the local and/or central laboratories (see Section 7.2.2.2).

During the Tapering and Follow-Up Period, if a subject meets the criteria for relapse, he will then proceed to the EOT Visit, at which  $t_{1/2}$  will be assessed.

CONFIDENTIAL

The information contained herein may not be used, disclosed, or published without the written consent of Bioverativ Therapeutics Inc.

Page 59

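### Protocol Table 2 footnote 4 sends subjects who develop inhibitors straight to end of treatment with no recovery condition, against the two-part relapse rule in Section 7.2.4

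*Protocol*

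**What the plan says.** Footnote 4 of Protocol Table 2 (Section 4.2) is attached to the Week 28 and Week 40 Follow-Up visits. Its second sentence is the exit rule at issue: "Subjects who develop inhibitors during the Tapering or the Follow-Up Period (i.e., who relapse) will proceed immediately to the ET/EOT Visit". It mentions neither IR nor a repeat test.

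Other places in the protocol and SAP bring IR into relapse or tie exit to relapse:

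- **Table 2 footnote 1**, on the Tapering Period, describes relapsing subjects as those "who have confirmation of inhibitor development AND who have confirmed decrease of IR, with or without clinical signs or symptoms".
- **Table 2 footnote 11**, covering both periods, says that if relapse is suspected "the test must be repeated at the following visit to confirm relapse (i.e., IR <66" percent).
- **Table 2, EOT column**, places the visit at Week 48 "following ITI success OR upon relapse".
- **Section 6.2** includes "abnormal recovery after tolerance is achieved" in the relapse endpoint, and adds a half-life below 7 hours.
- **Section 7.2.4, Relapse**, requires a titer of at least 0.6 BU/mL and an IR below 1.32 IU/dL per IU/kg, each on two consecutive assessments 2 to 4 weeks apart. It then states: "A subject with confirmed relapse (i.e., confirmation of both of the above criteria in 2 consecutive assessments) must complete the EOT Visit".
- **Section 7.2.5**: "A subject with confirmed relapse criteria will complete the EOT Visit as soon as possible".
- **Section 13.1.3.1**: "During the Tapering and Follow-Up Period, if a subject meets the criteria for relapse, he will then proceed to the EOT Visit".
- **SAP 4.4.1.1** defines relapse as a confirmed positive titer together with IR below 1.32.

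**The concern.** Footnote 4 is an operating instruction in the schedule that sites work from, and it decides whether a subject stays in the study. It gives a different answer from Section 7.2.4 for one kind of subject: positive titer, recovery still normal. Read literally, the footnote ends that subject's study treatment and observation, although neither Section 7.2.4 nor the SAP counts him as relapsed.

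The main stake is for the subject. The analysis has a smaller one: after an early exit, a later fall in IR would not be seen, and the subject would remain in the relapse analysis as a non-relapse.

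**Working it through.** **Comparison of the rules.** The plan states no figure to reproduce, so the check starts with the text. Take a subject in Follow-Up with a confirmed titer of at least 0.6 BU/mL and IR of at least 1.32.

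- Footnote 4: he has developed inhibitors, so he exits immediately.
- Section 7.2.4: the titer criterion is met and the IR criterion is not. There is no relapse, so no relapse-based exit.
- Sections 7.2.5 and 13.1.3.1 and the EOT column: exit follows relapse, so he stays.
- Footnote 11: relapse is confirmed through low IR, which he does not have.
- SAP 4.4.1.1: not a relapse.

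Footnote 1 contradicts footnote 4 directly, but its two-part wording covers only the Tapering Period. Among the Table 2 footnotes, footnote 4 is therefore the only one stating an exit rule for Follow-Up.

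**Follow-up lost.** Inputs are the Week 28, 40 and 48 visits (Table 2), the 48-week post-success period (Section 6.2), and the 2-to-4-week repeat interval (Section 7.2.4). Visit windows are ignored. Fraction lost = (48 − week of confirmation) / 48.

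Unscheduled repeat after 2 to 4 weeks, which footnote 8 says may be required:

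- First positive Week 28, confirmed Week 30 to 32: (48 − 30)/48 = 18/48 = 37.5%; (48 − 32)/48 = 16/48 = 33.3%.
- First positive Week 40, confirmed Week 42 to 44: (48 − 42)/48 = 6/48 = 12.5%; (48 − 44)/48 = 4/48 = 8.3%.

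Repeat at the next scheduled visit, since Section 7.2.4 and footnote 11 also say to repeat at the following visit:

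- First positive Week 28, confirmed Week 40: (48 − 40)/48 = 8/48 = 16.7%.
- First positive Week 40, confirmed Week 48: (48 − 48)/48 = 0.

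**Relapse proportion.** The denominator is the tapering-period analysis set (Protocol 16.2.2.2, SAP 4.4.1.2). The subject has entered tapering, so he stays in it. The SAP counts him as a non-relapse, so his exit alone changes nothing. If his IR would have fallen later, one relapse is missing from the numerator, so any change is downward.

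- About 17 subjects (Protocol 7.1), all entering tapering: 1/17 = 5.9 percentage points.
- 30 subjects (SAP Section 2), all entering tapering: 1/30 = 3.3 percentage points.

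The documents give no frequency for a positive titer with normal IR, or for a later loss of IR, so no expected effect can be calculated.

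**The case against.** The strongest reply is that footnote 4 is shorthand. Its parenthesis names relapse, a term defined under its own heading in Section 7.2.4, and Sections 7.2.4, 7.2.5 and 13.1.3.1 all tie exit to that term. An investigator who knows the protocol would probably apply the two-part rule. It is also fair to say that the footnote omits confirmation as well as IR, so context that supplies one should supply the other.

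Much of this stands as an account of intent, but it does not remove the conflict. The words equate relapse with developing inhibitors, and no text says that Section 7.2.4 prevails over the schedule. The inhibitor-only sense also occurs in Section 15.3.2, where a confirmed positive inhibitor after success is itself called relapse of an inhibitor. That section governs SAE reporting and sets no exit rule, but it shows that a site could read footnote 4 the same way.

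The reply is right about size. A reader might infer that about a third of post-success follow-up is at risk, or that a missed relapse costs at least 1/17. The documents support neither as a general figure. The larger losses need an unscheduled repeat visit, and the protocol's approximate 17 and the SAP's 30 leave 1/17 short of a firm minimum.

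A reader might also infer that one unconfirmed titer ends treatment, because the footnote asks for no repeat. Footnotes 8 and 11 provide for repeat testing, so the losses above are dated from a confirmed titer.

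**Conclusion.** The inconsistency is real. Footnote 4 gives an exit rule with no IR or confirmation condition, in conflict with the two-part rule in Section 7.2.4 and the related texts. It matters mainly because it could take a subject who has not relapsed off study treatment and observation.

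The size depends on when the titer is confirmed and on a site following the footnote over Section 7.2.4. The loss ranges from nothing (first positive at Week 40, confirmed at Week 48) to 18 of 48 weeks (first positive at Week 28, confirmed at Week 30).

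A reader might go further and infer that the relapse endpoint is compromised. The documents do not support that: SAP 4.4.1.1 fixes the definition whatever the footnote says, the endpoint is descriptive with no hypothesis test, and the listings in SAP 4.2 and 4.3.4 show the reason for early termination, time in follow-up and relapse status. The priority is low to moderate.

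**What to change.** Replace the second sentence of footnote 4 with: *Subjects with confirmed relapse as defined in Section 7.2.4 (2 consecutive positive titers AND 2 consecutive IRs <1.32 IU/dL per IU/kg, each within 2 to 4 weeks) during the Tapering or Follow-Up Period will proceed to the EOT Visit.*

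This can go in a clarification letter or the next amendment. It costs one reworded sentence, with no new visits, samples, tables or listings and no SAP change.
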